**H. Recruitment Procedures**

Describe the participants you intend to recruit. Provide all inclusion and exclusion criteria. Include age range, number of subjects, gender, ethnicity/race, socio-economic level, literacy level and health (as applicable) and reasons for exempting any groups. Describe how/when/by whom inclusion/exclusion criteria will be determined.

Participants will not be excluded based on sex, race, or ethnicity. If a participant is excluded for any reason, they will be immediately informed that they have not met all criteria and their participation will be discontinued. All interested participants will be selected to participate until the desired number ( $n = 80$  older adults) is reached. We recognize that women in this age group are over-represented relative to men and are also more likely to volunteer for health-related studies. However, we will do our best to recruit 50% women and 50% men in our sample.

Participants will be randomly assigned to one of the two study conditions. Children will not be included since the study is focused on older adults. Potential participants will be screened over the phone for cognitive function and will be assessed by the Telephone Interview of Cognitive Status (TICS) to ensure normal level of cognitive function. Any participant not passing the TICS as 'normal' will be ineligible for further consideration in the study. Participants with implanted devices that are likely to be adversely influenced by MRI will be marked as "MRI-ineligible" but may be able to participate in the remote/behavioral version of the study.

**Inclusion Criteria:**

- Men and women of all ethnicities/races and socio-economic status, 55-95 years

- Normal or corrected-to-normal vision based on the minimal 20/20 standard in order to complete the cognitive tasks
- 
- Able to speak, read, and write English
- Ambulatory without significant increase in pain or the assistance of walking devices
- No diagnosis of a neurological disease
- No contraindications to MRI imaging (if opting into MRI)
- Exercising less than 150 minutes per week (half of the recommended 150 minutes per week)  
AND sitting down more than 8 hours per day
- Regular access to a computer with internet
- Reliable transportation to the Northeastern University campus for 2 visits (if opting into MRI)
- Right-handed (if opting into MRI)
- Weight under 275 pounds (if opting into MRI)

#### Exclusion Criteria:

- Current or previous formal diagnosis of a DSM-V Axis I or II disorder including Major Depression (not including post-partum depression or anxiety)
- History of major psychiatric illness including schizophrenia
- Current treatment for cancer – except non-melanoma skin
- Neurological condition (MS, Parkinson's, Dementia, MCI) or brain injury (traumatic or Stroke)
- Type I Diabetes
- Type II Diabetes if unstable or controlled by insulin
- Current alcohol or substance abuse
- Current treatment for congestive heart failure, angina, uncontrolled arrhythmia, DVT or other cardiovascular condition
- A blood clot in the legs in the last 2 years
- Myocardial infarction, coronary artery bypass grafting, angioplasty or other cardiac event in the past year
- 
- Regular use of an assisted walking device or significant increase in pain when walking
- Claustrophobia (if opting into MRI)
- Not passing the Telephone Interview of Cognitive Status (TICS) as normal
- Use of any anti-psychotic, anti-depressant, anti-anxiety, and ADD/ADHD medications.
- Not fluent in English
- Contraindications to MRI (if opting into MRI)
- No regular access to a computer with internet
- Involvement in conflicting research studies currently or recently

#### Screening Procedures:

Screening procedures will involve verbally screening potential participants over the phone. A staff member doing the screening will begin with an overview of the DASH project. The screener will then obtain verbal consent (see telephone script). The telephone script will ask questions regarding potential participants' demographic information such as age and gender along with medical history questions in relation to inclusion and exclusion criteria. The total

time to administer all screening questions is approximately 30 minutes. The telephone screen will also assess level of physical activity via self-reported physical activity. If eligibility is verified, a date and time will be scheduled for a virtual meeting between the participant and a researcher where the formal study consent will be signed. Those individuals that are deemed ineligible from the screening call will have their forms kept in a separate file on REDCap. This information will be used to quantify how many were ineligible from the screening call and reasons for ineligibility.

The criteria will be assessed by one of the listed study personnel. No special expertise is required to evaluate screening responses. If a participant requires exclusion due to information received during a visit, they will be contacted via telephone or email and informed that they have been excluded from further study. The reason provided for their exclusion will be brief, and will include a statement such as, "Based on the data collected in your last session, we will not require any further testing. As indicated in the beginning, participation depends on a number of factors and not all participants qualify for the entire study."

Describe the procedures that you will use to recruit these participants. Be specific. How will potential subjects be identified? Who will ask for participation? If you intend to recruit using letters, posters, fliers, ads, website, email, PsyLink description, HIT, etc., copies must be included as attachments for stamped approval. Include scripts for intended telephone recruitment.

Older adult participants will be recruited through the local media (television, radio, newspapers), promotional flyers and targeted postcard mailings, announcements to local aging and senior citizen agencies, bus advertisements, online sites (e.g., Craig's list and Facebook), university registries, and announcements through local religious places of worship. All of the above recruitment strategies will use the same language as attached flyer and social media ads.

#### What remuneration, if any, is offered?

Remuneration will be offered as follows:

VISIT	Approx. Hours	Approx. Pay
T1	4	\$80
T2	3	\$60
T3	3	\$60
T4	2	\$40
Accelerometry Completion	N/A	\$100
TOTALS	12 hours	\$240 without accelerometry completion, \$340 with. Less if

		the participant opts out of MRIs.
--	--	--

Participants will be paid \$20/hour for study activities including cognitive and behavioral assessments, physical assessments, and MRIs. The time they spend on each activity may be slightly variable due to whether they opt into MRIs, their speed completing tasks and other, everyday factors, so individuals may spend about 12-18 hours on the study and will be paid accordingly. They will be paid after each of the four main study visits through a check that will be sent to them through the mail, but exceptions will be made in payment schedule for those who request it (in order to alleviate any concerns with Social Security interference). Participants will fill out a W-9 tax form at the time of consent to allow for their payment. If they finish the study and complete all parts, including wearing the physical activity monitoring devices consistently, responding to daily messages, and returning the devices at the end of the study, they will be able to earn an extra \$100.

If the participant attempts but is unable to complete the scan (e.g., scanner issue, claustrophobia, etc.), they will be compensated in full for that particular scan.

## **I. Consent Process**

Describe the process of obtaining informed consent\*. Be specific. How will the project and the participants' role be presented to potential participants? By whom? When? Where? Having the participant read and sign a consent statement is done only after the researcher provides a detailed oral explanation and answers all questions. Please attach a copy of informed consent statements that you intend to use, if applicable. [Click here for consent form templates.](#)

If your study population includes non-English speaking people, translations of consent information are necessary. Describe how information will be translated and by whom. You may wait until the consent is approved in English before having it translated.

Participants' consent will be obtained remotely before they begin participating in research activities. The consent process will be administered by experimenters (i.e., research personnel described above). Individuals who agree to participate after the phone screen will receive a copy of the consent document in advance and will schedule a time to speak with an experimenter over the phone. They will be asked to read, but not sign, the consent document before the phone call, and the experimenter will coordinate with the participant so they have enough time to read the document before the call. During the call, the experimenter will explain the study and answer any questions the participant has. If the participant wants to continue with the study, they will then sign the consent document electronically in REDCap. Participants will be made aware that their participation is completely voluntary and they may quit the experiment at any time.

If your population includes children, prisoners, people with limited mental capacity, language barriers, problems with reading or understanding, or other issues that may make them vulnerable or limit their ability to understand and provide consent, describe special procedures that you will institute to obtain consent appropriately. If participants are potentially decisionally impaired, how will you determine competency?

N/A

**\*If incomplete disclosure during the initial consent process is essential to carrying out the proposed research, please provide a detailed description of the debriefing process. Be specific.** When will full disclosure of the research goals be presented to subjects (e.g., immediately after the subject has completed the research task(s) or held off until the completion of the study's data collection)? By whom? Please attach a copy of the written debriefing statement that will be given to subjects.

Complete disclosure will be provided during the consent process.

#### **J. Study Procedures**

Provide a detailed description of all activities the participant will be asked to do and what will be done to the participants. Include the location, number of sessions, time for each session, and total time period anticipated for each participant, including long term follow up.

#### **PARTICIPANTS:**

In 80 sedentary and cognitively asymptomatic older adults (60 – 95 years) we will test whether a behavioral intervention combining self-affirmations and gain-framed health messages decreases the amount of time participants are sedentary, as measured by accelerometry. Participants completing MRIs will be in the “MRI group,” while those who do not will be in the “behavioral group.” We will use stratified randomization to be sure that half of the participants in each group will be randomized to the self-affirmation + gain-framed health messaging condition (intervention) and the other half will be randomized to a loss-framed health messaging only condition (control). Participants will not be explicitly told to exercise as part of the study, but during the experiment they will receive messages that encourage walking or decreasing sedentary time. The primary measure of interest is decrease in sedentary behavior. All participants will be recruited and screened remotely by researchers affiliated with the Center for Cognitive & Brain Health in the Interdisciplinary Science and Engineering Complex under the direction of Drs. [name], [name] and [name].

In addition to these 80 participants, we will recruit up to 20 pilot participants who will complete smaller portions of the study and whose data will only be used to improve design.

#### **PERSONNEL:**

All staff and personnel associated with screening, collecting data, and analyzing data will have been trained in their laboratory and will have undergone all necessary research modules for safety and research ethics. [name] will meet with all staff on a regular basis to ensure that they are conducting research protocols appropriately. In addition, all staff who interact with participants will be certified in AED and CPR. All staff who administer remote study visits will be familiar with an emergency protocol (including calling emergency services) to prepare for the unlikely event that a participant has a medical emergency during a video or phone appointment. MRI data will be collected by licensed MR technicians and staff trained to analyze MRI scans.

## RESEARCH ACTIVITIES:

### Overview:

There will be a total of --- visits, with each visit split into multiple sessions. Participants will complete neuropsychological and behavioral inventories, cognitive tests, writing tasks, and computer tasks at these visits. There will also be 2 visits, one before intervention and one after dedicated to physical assessments. Additionally, participants opting into the MRIs will come in-person before and after intervention for the MRI. Outside of the sessions, participants will wear two accelerometry devices for 4 separate weeks in the study and receive and respond to daily messages as part of the intervention. Each of these aspects and what they entail is detailed below.

### Surveys:

During the first visit, known as “Consent Visit 1”, participants will sign the consent form, complete the W-9 form and complete surveys. Participants will complete screening measures for anxiety, depression, and cognitive impairment. If they pass these screenings, they will be randomized into the intervention (self-affirmation + gain-framed messaging) or control group (loss-framed messaging only). In this visit and the next (Consent Visit 2) they will also complete neuropsychological and behavioral inventories. We expect testing to take about 3 hours total over the 2 sessions and will administer the assessments with breaks every ~40 minutes to reduce fatigue. They will complete behavioral inventories that capture individual differences in traits potentially predicting responsiveness to the intervention. These measures (listed in the attached spreadsheet) include validated questionnaires to assess factors like motivation for physical activity, self-efficacy for exercise, self-efficacy for walking, barriers to exercise, mood, conscientiousness and grit, growth mindset, loneliness, future time perspective, and purpose in life. Participants’ educational attainment and total personal income levels will also be collected to create a measure of socioeconomic status, as described by Hartanto et al. (2019). These questionnaires will be administered through REDCap, a “secure, HIPAA-compliant, web-based application... housed in a secure local data center, behind the Tufts Medical Center firewall, and all web-based information is encrypted” ([tuftsctsi.org/research-services/informatics/redcap-research-electronic-data-capture/](http://tuftsctsi.org/research-services/informatics/redcap-research-electronic-data-capture/)).

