#### Accelerometry:

Participants will be fitted with two accelerometers and have their cardiorespiratory status estimated. The estimation uses a regression equation that includes age, sex, body mass index, and resting heart rate. We will obtain a non-exercise CRF estimation before and after the six-week intervention. To perform the CRF estimation, which will be remote, we will ask participants to report their supine resting heart rate (i.e., the average of all R-R intervals over ten seconds) after they have rested quietly for ten minutes. Participants will also complete a physical assessment focused on their basic walking speed, their ability to transition repeatedly from sitting to standing, and their balance.

Accelerometers, chargers, and related materials will be sent to participants through the mail after the consent meeting and will be returned after the 3-month follow-up session. Accelerometry data will be recorded during wakefulness and sleep, with the exception of bathing or swimming, for the week between the Red and Orange visits (before the intervention begins; i.e., baseline), for two separate weeks during the 6-week intervention (with additional days during this timeframe for any participant who does not wear the devices consistently during the original period), and for a week after the 3-month follow-up visit. This will characterize change in physical activity from baseline and maintenance. It will be assessed using two accelerometers worn simultaneously. The first is a wrist-worn tri-axial accelerometer (ActiGraph GT3X Link, Pensacola, FL). This accelerometry data will be downloaded in 60-second epochs (ActiLife software, ActiGraph, Pensacola, FL) and will be screened for wear time using standard methods (Choi et al., 2011). The second device is a tri-axial accelerometer and inclinometer (activPAL) and will be worn on the thigh using an adhesive.

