158 such as Craigslist and Facebook. Potential participants are screened by phone. The Telephone
159 Interview of Cognitive Status (TICS) is used initially to screen cognitive function. Sitting Time
160 questionnaire [27] and International Physical Activity Questionnaire [28] are used for screening
161 physical activity engagement and sedentary behavior. Potential participants are asked a series of
162 questions relating to the inclusion/exclusion criteria and past medical history.
163

164 **Intervention**

165 ***Study timeline***

166 An illustration of the study timeline can be seen in Figure 1. Each participant undergoes a
167 baseline session (T1) one week before the beginning of the intervention. Informed consent is
168 obtained at baseline, during which participants specify whether they opt to participate in the MRI
169 scans or not. Randomization takes place after obtaining informed consent (T1) and participants
170 are assigned into either the intervention or control group. During the T1 visit, the participants
171 also undergo baseline testing including neuropsychological tests and neurobehavioral
172 inventories, which take about 3 hours in total. In order not to prime exercise for the baseline
173 physical activity level, inventories that are related to exercise and self-perception are not
174 administered during T1 visit. At baseline, participants wear an activPAL monitor on their thigh
175 to assess postural aspects of sedentary behavior including time spent sitting and lying and a
176 wrist-worn accelerometer on their non-dominant hand to assess physical activity (see physical
177 activity monitoring). Both monitors are worn for a week. One week later (T2), physical
178 assessments and the remaining neurobehavioral inventories related to exercise and self-
179 perception will be administrated, which takes about 1.5 hours. The intervention lasts 4 weeks,
180 during which participants receive daily intervention messages via email or smartphone.
181 Participants are fitted with the accelerometers again for a one-week mid-intervention period
182 (week 3). The post-intervention visit (T3) is scheduled at the beginning of the last intervention
183 week (week 4). After the last intervention week (T4), participants repeat the neurobehavioral
184 week (week 4). After the last intervention week (T4), participants repeat the neurobehavioral
185 week (week 4). After the last intervention week (T4), participants repeat the neurobehavioral

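### On a plain reading, the protocol gives the exercise-related questionnaires before the baseline device week; the SAP holds them back until after it to avoid priming

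*Protocol*

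**What the plan says.** **Protocol, section J, Surveys.** After describing consent and randomisation at Consent Visit 1, the text continues: "In this visit and the next (Consent Visit 2) they will also complete neuropsychological and behavioral inventories". It adds "We expect testing to take about 3 hours total over the 2 sessions". The behavioural measures are then said to "include validated questionnaires to assess factors like motivation for physical activity, self-efficacy for exercise, self-efficacy for walking, barriers to exercise", followed by mood, grit, loneliness, purpose in life and others. No measure is deferred to a later visit, and priming is not mentioned. The full list is referred to an attached spreadsheet.

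**Protocol, section J, Accelerometry.** Devices and materials "will be sent to participants through the mail after the consent meeting". Baseline recording is "for the week between the Red and Orange visits (before the intervention begins; i.e., baseline"). The calendar at the end of section J puts the consent visit in a column before Week 0 (shipping) and before the first device week.

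**SAP, Study timeline.** For the sake of an unprimed baseline "physical activity level, inventories that are related to exercise and self-perception are not" given at T1. Monitors are worn for a week after T1. The withheld inventories are given at T2, one week later, together with the physical assessments, in a session of about 1.5 hours.

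**The concern.** The two documents put the same questionnaires on opposite sides of the baseline device week, and the SAP gives a reason for its order. Staff working from the protocol text alone would not apply a protection that the SAP authors thought necessary.

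Baseline is the reference for much of what the trial intends to report. The protocol's outcome table describes step count, sedentary time and the secondary activity measures as change from baseline. The first hypothesis in section E is partly a within-arm statement: activity rises with self-affirmation plus gain framing and does not rise with loss framing alone. The Daily Messaging section repeats that only the intervention arm is expected to increase from baseline. If answering questions about exercise motives, confidence and barriers makes people less sedentary in the monitored week that follows, the baseline is no longer habitual behaviour. A real fall in sedentary time would then be understated in the intervention arm, and an unchanged control arm could appear to get worse.

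**Working it through.** The documents state no figure on this point, so there is nothing to reproduce. The SAP's sample size rests on a between-arm difference at week 4 and does not depend on the order of questionnaires. The check sets the sequences side by side and then works out in symbols what each order does to change from baseline.

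**1. Sequence**

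| Step | Protocol, section J | SAP, Study timeline |
|---|---|---|
| First testing | Consent Visits 1 and 2, about 3 hours; behavioural inventories, exercise items named, none deferred | T1, about 3 hours; exercise and self-perception inventories excluded |
| Devices | Posted after consent; baseline week follows | Worn for one week after T1 |
| After the baseline week | No statement that exercise inventories wait until now | T2: exercise and self-perception inventories, about 1.5 hours with physical assessments |

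The protocol's consent visits need not be identical to the SAP's T1. It is enough that they come before device wear, and under the protocol's own shipping rule and calendar they do.

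**2. Effect on change from baseline**

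All quantities are percentage points of waking time. Let H be habitual sedentary time, D the fall an arm would show without any questionnaire effect, and p the fall that the questionnaires cause at first. Let r be the share of p still acting in a later device week when they are given before baseline, and s the same share when they are given at T2.

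- Protocol order: baseline = H − p; later week = H − D − rp; recorded fall = (H − p) − (H − D − rp) = D − (1 − r)p.
- SAP order: baseline = H; later week = H − D − sp; recorded fall = D + sp.
- Between-arm difference in recorded fall: D(intervention) − D(control) under either order, provided p, r and s are the same in both arms.

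**3. Illustration only**

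The documents give no value for p, r or s. Assume p = 1 to 3. For scale, set D = 10, a figure borrowed from the SAP's between-arm target, which is not itself a within-arm change.

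| Share still acting | Protocol order, recorded fall | SAP order, recorded fall |
|---|---|---|
| 0 | 10 − 1 = 9 to 10 − 3 = 7 | 10 |
| 0.5 | 10 − 0.5 = 9.5 to 10 − 1.5 = 8.5 | 10 + 0.5 = 10.5 to 10 + 1.5 = 11.5 |
| 1 | 10 | 10 + 1 = 11 to 10 + 3 = 13 |

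For a control arm with D = 0, p = 3 and r = 0, the protocol order records 0 − 3 = −3, an apparent rise of 3 points. The between-arm difference is still 7 − (−3) = 10.

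**The case against.** The SAP half is explicit; the protocol half is an inference. One sentence places behavioural inventories at the consent visits. A later sentence, with no visit attached, lists the exercise measures and points to the spreadsheet. Elsewhere section J says that the spreadsheet's assessments are given at T1, T2, T3 and/or T4, so the spreadsheet may already put the exercise items at T2. This stands as a caveat. It does not remove the point: the protocol text never says so, and its natural reading contradicts the SAP.

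The matching 3-hour figures do not prove that the consent visits are the SAP's T1. The calendar shows the consent visit separately from Week 0, and the payment table gives T1 as 4 hours. This is correct, but the order relative to device wear does not rest on it.

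The SAP's protection is only partial. Phone screening already asks about physical activity in both documents, and the SAP also uses a sitting-time questionnaire there. The protocol also promises complete disclosure at consent. Any added effect of the motivation, confidence and barriers questionnaires may therefore be modest.

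Moving questionnaires to T2 is not free of bias. Any priming then falls between baseline and follow-up and can inflate within-arm change in both arms, as the SAP-order column shows. This stands and should be acknowledged.

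A reader might also infer that some participants followed one order and some the other, leaving baselines that are not comparable. Nothing in the documents suggests mixed practice; the study is run by one laboratory.

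**Conclusion.** The conflict holds on the plain reading of the protocol, subject to the unseen spreadsheet. It should be corrected because the SAP itself identifies the risk, but its reach is limited.

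A reader might infer that the primary randomised comparison is biased. The documents do not support that. The SAP's primary analysis is a group-by-time mixed model, both arms receive the same inventories, and a shift common to both arms cancels. The comparison is largely rather than wholly spared, because cancellation assumes that priming and its fading are the same in each arm.

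What is exposed is baseline as a measure of habitual behaviour, together with the within-arm statements in section E, Daily Messaging and the outcome table. The size is unknown. A loss of 1 to 3 points from a 10-point fall is not a finding: it needs an assumed effect, in an assumed direction, that has vanished entirely by follow-up. If the effect persists in full, change from baseline is not altered at all under the protocol order.

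**What to change.** Amend section J, Surveys, and the instrument spreadsheet if it differs, so that the inventories related to exercise and self-perception are given at T2, after baseline wear and before the first message, as the SAP states. Name the visit for each of these instruments. Move only these. Mood, grit, loneliness, purpose in life and similar inventories may stay at the consent visits unless the sponsor classes them as self-perception; the SAP does not ask for more.

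Add a sentence to the analysis plan acknowledging that questionnaires at T2 may contribute to change in both arms, that within-arm change is to be read cautiously, and that the conclusion rests on the between-arm contrast. If participants have already been assessed, document which order was used.

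The cost is a wording change and the reassignment of existing REDCap forms to another visit. If only these inventories move, no extra participant time is needed, because the SAP's T2 session of about 1.5 hours already includes them.
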